10.3 Dose Reductions for Hepatic Impairment

Hepatic impairment will be classified by the NCI Organ Dysfunction Working Group criteria. Any hepatic dysfunction classified as moderate or severe will require the treating physician to hold study drug until two weeks after hepatic dysfunction can be classified as mild or normal by NCI criteria. Ruxolitinib may be restarted at 50% of the MTD. If moderate or severe hepatic impairment occur a second time in the same subject, ruxolitinib will be discontinued.

11 ADVERSE EVENTS: REPORTING REQUIREMENTS

The investigator or site staff will be responsible for detecting, documenting and reporting events that meet the definition of an AE or serious adverse event (SAE).

To ensure patient safety, each SAE must be reported to the coordinating site and to Incyte ([contact]) on the Incyte form provided within 24 hours of being made aware of the event. Moffitt Cancer Center and all participating sites will report SAEs by completing an SAE report in OnCore, the electronic data capture system. The SAE must be reported by email ([contact]) to the External Site Coordination (ESC) office within 24 hrs. If applicable, the site should also follow protocol guidelines for additional reporting to government agencies.

11.1 Definition of an AE

Any untoward medical occurrence in a subject or clinical investigation subject, temporally associated with the use of a medicinal product, whether or not considered related to the medicinal product. Note: An AE can therefore be any unfavorable and unintended sign (including an abnormal laboratory finding), symptom, or disease (new or exacerbated) temporally associated with the use of a medicinal product.

Events meeting the definition of an AE include:

- Exacerbation of a chronic or intermittent pre-existing condition including either an increase in frequency and/or intensity of the condition.
- New conditions detected or diagnosed after investigational product administration even though it may have been present prior to the start of the study.
- Signs, symptoms, or the clinical sequelae of a suspected interaction.
- Signs, symptoms, or the clinical sequelae of a suspected overdose of either investigational product or a concomitant medication (overdose per se will not be reported as an AE/SAE). “Lack of efficacy” or “failure of expected pharmacological action” per se within the duration of initial ruxolitinib treatment/exposure of 16 weeks will not be reported as an AE or SAE. However, the signs and symptoms and/or clinical sequelae resulting from lack of efficacy will be reported if they fulfill the definition of an AE or SAE.

Events that **do not** meet the definition of an AE include:

- Medical or surgical procedure (e.g., endoscopy, appendectomy); the condition that leads to the procedure is an AE.
- Situations where an untoward medical occurrence did not occur (social and/or convenience admission to a hospital).
- Anticipated day-to-day fluctuations of pre-existing disease(s) or condition(s) present or detected at the start of the study that do not worsen.
- The disease/disorder being studied or expected progression, signs, or symptoms of the disease/disorder being studied, unless more severe than expected for the subject's condition.
- Death due to the disease being studied.

11.2 Definition of an SAE

A serious adverse event is any untoward medical occurrence that, at any dose:

- Results in death
- Is life-threatening

NOTE: The term “life-threatening” the definition refers to an event in which the subject was at risk of death at the time of the event. It does not refer to an event, which hypothetically might have caused death, if it were more severe.

- Requires hospitalization or prolongation of existing hospitalization.

NOTE: In general, hospitalization signifies that the subject has been detained (usually involving at least an overnight stay) at the hospital or emergency ward for observation and/or treatment that would not have been appropriate in the physician's office or out-patient setting. Complications that occur during hospitalization are AEs. If a complication prolongs hospitalization or fulfills any other serious criteria, the event is serious. When in doubt as to whether “hospitalization” occurred or was necessary, the AE should be considered serious. Hospitalization for elective treatment of a pre-existing condition that did not worsen from baseline is not considered an AE.

- Results in disability/incapacity

NOTE: The term disability means a substantial disruption of a person's ability to conduct normal life functions. This definition is not intended to include experiences of relatively minor medical significance such as uncomplicated headache, nausea, vomiting, diarrhea, influenza, and accidental trauma (e.g. sprained ankle) which may

interfere or prevent everyday life functions but do not constitute a substantial disruption.

- Is a congenital anomaly/birth defect
- All treatment related grade 4 non-hematologic laboratory abnormalities assessed using the National Cancer Institute (NCI) Common Terminology Criteria for Adverse Events (CTCAE) v 4.0.

Medical or scientific judgment should be exercised in deciding whether reporting is appropriate in other situations, such as important medical events that may not be immediately life-threatening or result in death or hospitalization but may jeopardize the subject or may require medical or surgical intervention to prevent one of the other outcomes listed in the above definition. These should also be considered serious. Examples of such events are invasive or malignant cancers, intensive treatment in an emergency room or at home for allergic bronchospasm, blood dyscrasias or convulsions that do not result in hospitalization, or development of drug dependency or drug abuse.

11.3 Relationship to Investigational Product

It is a regulatory requirement for investigators to assess relationship to investigational product based on information available. The assessment should be reviewed on receipt of any new information and amended if necessary. “A reasonable possibility” is meant to convey that there are facts/evidence or arguments to suggest a causal relationship. Facts/evidence or arguments that may support “a reasonable possibility” include, e.g., a temporal relationship, a pharmacologically-predicted event, or positive dechallenge or rechallenge. Confounding factors, such as concomitant medication, a concurrent illness, or relevant medical history, should also be considered.

11.4 Laboratory and Other Safety Assessment Abnormalities Reported as AEs and SAEs

Any abnormal laboratory test results (hematology, clinical chemistry, or urinalysis) or other safety assessments (e.g., ECGs, radiological scans, vital signs measurements), including those that worsen from baseline should be recorded as per the NCI-CTC AE criteria. However, these laboratory results are to be recorded as AEs or SAEs if deemed clinically significant in the medical and scientific judgment of the

investigator or treating physician. Any clinically significant safety assessments that are associated with the underlying disease are **not** to be reported as AEs or SAEs, except for findings judged by the investigator or treating physician to be more severe than expected for the subject's condition or death. Data will be collected for typical disease-related events such as anemia, leukocytopenia or worsening of thrombocytopenia. All infections experienced during the study are to be recorded as AEs or SAEs.

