Treatment plan	
Treatment will be administered on an outpatient basis. Reported adverse events and potential risks are described in Section 11. Appropriate dose modifications for ruxolitinib are described in Section 10. No investigational or commercial agents or therapies other than those described below may be administered with the intent to treat the patient's CMML. Ruxolitinib will be supplied by INCYTE as 5mg tablets. .
 
Ruxolitinib will be self-administered as a twice-daily oral dose for a continuous treatment cycle. Ruxolitinib tablets will be taken approximately 12 hours apart (morning and night). Patients will not take the morning dose of ruxolitinib at the first regularly scheduled visit.. On all other days corresponding to study visits, patients will take the morning dose of study drug prior to the visit, and will note on the subject reminder card the time that medications were taken.
 
Patients will also be instructed to take ruxolitinib without respect to food, as previous data demonstrate no change in drug kinetics or absorption. All patients will be given 40 mg/day divided in equal BID doses. A maximum of 29 patients will be treated at the MTD identified in phase I of 20mg BID. See study calendar for assessment on study.

Dose delay/modifications	
Dose delays/modifications are allowed for those patients enrolled in phase II as described in section 6.

Duration of Therapy	
Patients will be treated for a total of 16 weeks. For patients responding at week 16, treatment may continue until one of the following criteria applies:
 
 • Intercurrent illness that prevents further administration of treatment. • Unacceptable adverse event(s). • Patient decides to withdraw from the study. • General or specific changes in the patient's condition render the patient unacceptable for further treatment in the judgment of the investigator. • Evidence of disease progression by the IWG MDS/MPN criteria.

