During the Phase I and Phase II development program, ruxolitinib was assessed in healthy volunteers, patients with various degrees of renal or hepatic impairment, in patients with rheumatoid arthritis, prostate cancer, multiple myeloma, myelofibrosis (MF), polycythemia vera (PV) and essential thrombocythemia (ET). The aggregate safety database for ruxolitinib included 679 patients treated in 6 studies. Hematologic events were the most frequently reported adverse events (AE)s however, the majority of these were of Grades 1-2, seldom leading to study drug discontinuation (<1% of patients). Increased rates of anemia did result in an increase in packed red blood cell (PRBC) transfusion requirements for some ruxolitinib-treated patients but platelet transfusions while on ruxolitinib were rare. No Grade 4 events as it relates to biochemistry laboratory abnormalities of alanine aminotransferase (ALT), aspartate aminotransferase (AST) or cholesterol were reported. The Phase III safety dataset in MF patients shows that it was appropriate to individually adjust doses for patients according to their tolerability and efficacy. However, 124 patients (41.2%) required no dose reduction, indicating the starting dose of 15mg or 20mg BID was appropriate for these individuals. Of the 177 patients who had dose reduction, 91 patients (51%) had only one. Interruptions of dosing were less frequent than dose reductions, with 215 patients (71.4%) requiring no dose interruption. Of the 86 patients who had dose interruptions, 59 patients (19.6%) had only one dose interruption. The Phase III safety dataset in MF patients showed that the only notable imbalances (ruxolitinib versus placebo or best available therapy [BAT]) in AEs related to hemorrhagic events were in Grade 1-2 skin and soft tissue bruising which did not lead to dose reduction or discontinuation. Similarly, the only notable imbalances (ruxolitinib versus placebo or BAT) in AEs related to infections were urinary tract infections and herpes zoster infections. A thorough QT study was conducted in 50 healthy patients. There was no indication of a QT/QTc prolonging effect of ruxolitinib in single doses up that exceeded those proposed in this study¹⁷.

Efficacy

In two large phase 3 clinical trials, ruxolitinib has demonstrated efficacy in patients with high-risk myelofibrosis. The first trial randomly assigned patients to receive

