5 STUDY DESIGN

This is a phase 2, Simon's two stage design. A total of 10 patients will be treated during the first stage of phase 2 (stage 1) at 20mg BID. The trial will be terminated if 1 or fewer respond. If the trial goes on to the second stage, a total of 29 patients will be studied to determine efficacy in phase 2.

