11.5 Disease-Related Events and/or Disease-Related Outcomes Not Qualifying as SAEs

During the study period, the following conditions will not qualify as an AE or SAE provided they are not considered attributable to study medication:

- Cases of disease progression.

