11.7 Time Period and Frequency of Detecting AEs and SAEs

The investigator or site staff is responsible for detecting, documenting and reporting events that meet the definition of an AE or SAE. AEs will be collected from the start of Investigational Product and through the follow-up contact. SAEs will be collected

over the same time period as stated above for AEs. However, any SAEs assessed **as related** to study participation (e.g., investigational product, protocol mandated procedures, invasive tests, or change in existing therapy) will be recorded from the time a subject consents to participate in the study up to and including any follow-up contact. All SAEs will be reported to INCYTE [contact] within 24 hours, as indicated.

11.8 Prompt Reporting of Serious Adverse Events and Other Events to the FDA with notification to INCYTE

Any serious adverse events which occur during the clinical study or within 30 days of receiving the last dose of study medication, whether or not related to the study drug, must be reported by the investigator. In addition, any SAEs which occur as a result of protocol specific diagnostic procedures or interventions must also be reported. SAEs brought to the attention of the investigator at any time after cessation of ruxolitinib and considered by the investigator to be related or possibly related to ruxolitinib must be reported to FDA with notification to INCYTE [contact] if and when they occur. Additionally, in order to fulfill international reporting obligations, SAEs that are related to study participation (e.g., procedures, invasive tests, change from existing therapy) or are related to a concurrent medication will be collected and recorded from the time the subject consents to participate in the study until he/she is discharged.

Type of Event	Initial Reports		Follow-up Information on a Previous Report	
	Time Frame	Documents	Time Frame	Documents
All SAEs	24 hours*	“SAE” data collection tool	24 hours*	Updated “SAE” data collection tool
Pregnancy	2 Weeks*	Pregnancy Notification Form	2 Weeks*	Pregnancy Follow-up Form

- From the time point when the SAE or pregnancy became known to reporter.

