15.4 Safety Analysis

This analysis will include all patients who have received any protocol treatment, regardless of patient eligibility. The number (%) of patients with adverse events, serious adverse events, and adverse events leading to treatment discontinuation will be reported. Adverse events summary will be reported by type and severity. Laboratory parameters will also be summarized using descriptive statistics. The number and proportion of patients with DLTs will be summarized.

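### AE and SAE counts for cytopenias depend on an attribution to CMML that a single-arm trial cannot check, and Section 11 contradicts itself on whether a disease death is an SAE

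*Combined protocol and SAP*

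**What the plan says.** **Cytopenias.** Section 11.4 states: "Any clinically significant safety assessments that are associated with the underlying disease are" not to be reported as AEs or SAEs. It excepts findings that the investigator or treating physician judges more severe than expected for the patient's condition, and death. Section 11.1 likewise excludes expected progression, signs and symptoms of the disease unless more severe than expected. Section 11.4 also requires abnormal laboratory results to be recorded by NCI-CTC AE criteria, requires data on anemia, leukocytopenia and worsening thrombocytopenia to be collected, and keeps every infection as an AE or SAE.

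**Deaths and progression.** Section 11.1 lists "Death due to the disease being studied" among the events that are not AEs. Section 11.2 makes any untoward occurrence that results in death an SAE, with no exception for the disease. Section 11.8 says that SAEs during the study or within 30 days of the last dose, "whether or not related to the study drug, must be reported by the investigator". Section 11.5, whose only listed condition is disease progression, says that "the following conditions will not qualify as an AE or SAE provided they are not considered attributable to study medication".

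**Analysis.** Section 15.4 covers all treated patients: "The number (%) of patients with adverse events, serious adverse events, and adverse events leading to treatment discontinuation will be reported". AEs are also summarized by type and severity. Laboratory parameters get descriptive statistics. No death table is named.

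**Context.** Section 5: "This is a phase 2, Simon's two stage design". The synopsis adds: "A maximum of 29 patients will be treated at the MTD identified in phase I of 20mg BID". There is no comparator.

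**The concern.** The disease and the drug produce the same events. Section 2.1 describes CMML by its cytopenias, and Section 2.3 says of ruxolitinib: "Hematologic events were the most frequently reported adverse events". Entry allows platelets down to 35,000/uL and ANC down to 250/uL (Section 4.2.1), so many falls in count will start from an already low level. Whether such a fall becomes an AE turns on two judgements: whether it is associated with CMML, and whether it is more severe than expected. The plan does not define what is expected. A control arm would supply a background rate against which to test those judgements; this trial has none.

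A cytopenia judged disease-related and expected drops out of the AE count, the SAE count and the AE severity summary, so any error from this source makes the drug look safer. The monthly committee review in Section 17.6 also works from AEs and may not see these events.

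For deaths, the difficulty is contradictory instructions. Two sites could record the same CMML death differently, and both could cite the protocol.

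**Working it through.** The plan states no figure on this point, so there is none to reproduce. The check is a comparison of sections, followed by two illustrations of size.

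**Step 1. Where a CMML-associated cytopenia goes**

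| Destination | Reached? | Source |
|---|---|---|
| AE or SAE count and AE severity summary | Only if judged more severe than expected | 11.1, 11.4, 15.4 |
| Record by NCI-CTC AE criteria | Yes | 11.4 |
| Weekly CBC to week 16 | Yes | 13.2.1 |
| Laboratory summary | Yes, but no grade, worst value or baseline shift specified | 15.4 |
| Named table for the separately collected cytopenia data | None named | 11.4, 15.4 |

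The data exist. The counts are filtered by attribution, and the unfiltered summary is not specified in a form that shows toxicity.

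**Step 2. How far the AE count could move (assumed inputs)**

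Let T be the true share of patients with a new or worse cytopenia and f the share of those attributed to CMML and left out. The reported share is T × (1 − f). The documents give neither T nor f.

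| T | f = 0 | f = 0.25 | f = 0.50 | f = 0.75 |
|---|---|---|---|---|
| 0.30 | 30% | 22.5% | 15% | 7.5% |
| 0.50 | 50% | 37.5% | 25% | 12.5% |
| 0.70 | 70% | 52.5% | 35% | 17.5% |

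At T = 0.50 and f = 0.50, the true number is 29 × 0.50 = 14.5 patients and the reported number 29 × 0.25 = 7.25. Seven of 29 is 24%, exact 95% CI 10% to 44%. At f = 0 there is no under-count.

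**Step 3. Is a CMML death in week 10 an SAE?**

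- 11.1: no; it is not even an AE.
- 11.2: yes; it results in death.
- 11.4: its disease exclusion does not apply, because death is excepted.
- 11.8: an SAE in this window is reportable whatever its cause. But 11.8 acts only on events already classed as SAEs, so it does not settle whether 11.1 or 11.2 governs.
- 11.5: if the death is recorded as progression, the test becomes attribution to the drug, whereas 11.1 tests progression by whether it is more severe than expected.

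No order of precedence is given.

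**Step 4. How many deaths could meet the conflict**

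Inputs: median survival m of 12 to 20 months (Section 2.1); 16 weeks of treatment (Section 7); 30 days (Section 11.8); N = 29 (synopsis). Exponential survival is an assumption.

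- t = (16 × 7 + 30) / 30.44 = 142 / 30.44 = 4.67 months.
- Probability of death by t: q = 1 − 2^(−t/m).
- m = 12: q = 0.236; 29q = 6.85 patients.
- m = 20: q = 0.149; 29q = 4.33 patients.

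To week 16 alone, the same formula gives 5.6 and 3.5 patients.

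This is all-cause mortality, so deaths due to CMML can only be fewer. Entry requires a life expectancy over 3 months (Section 4.1.8), which lowers the figure; patients who stop early also leave the 30-day window sooner. Responders who continue past week 16 stay in the window longer, so the figure covers only deaths by that date.

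**The case against.** There are several good points on the plan's side.

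- Section 11.4 keeps cytopenia results on record by CTC criteria whatever their cause, and the laboratory summary in 15.4 is not filtered by attribution.
- Other text pulls toward reporting. Section 11.1 counts exacerbation of a pre-existing condition as an AE. Section 11.2 names blood dyscrasias without hospitalization among examples of serious events. Section 11.3 treats timing and pharmacological prediction as support for drug causality.
- Deaths remain visible: overall survival is a secondary endpoint (3.2.2), date of death is recorded off study (13.7), and cause of death is sought every 6 months (10.1).
- No objective or endpoint is a safety measure, and the two-stage decision rule does not use AE counts.

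All of this stands, and it rules out stronger readings that a reader might infer. The documents do not support saying that cytopenias and deaths are removed from the safety data, or that the safety tables as a whole under-count: only the AE and SAE counts are exposed, and on deaths only 11.1 is a plain exclusion. Nor does 11.1 exclude progression outright; it excludes expected progression that is not more severe than expected.

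The objection does not answer two things. Descriptive statistics on blood counts need not show how many patients reached a given grade or worsened from baseline. And collecting deaths for survival does not tell a site whether to file an SAE.

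**Conclusion.** The point holds as a risk to the AE and SAE counts, together with a plain contradiction on disease deaths. It should be corrected, but it does not touch the efficacy decision.

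The cytopenia under-count has a known direction and an unknown size. It could be zero, and the table of assumed values shows only how sensitive the count is. For deaths, about 4 to 7 of 29 patients is the expected all-cause number by 30 days after week 16, given exponential survival, the protocol's general median for CMML, and no adjustment for the entry criteria. It would be wrong to read this as 4 to 7 deaths missing from the trial: it caps the deaths exposed to conflicting instructions by that date, and vital status and cause are collected elsewhere.

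**What to change.** 1. In Section 15.4, tabulate the worst post-baseline CTCAE grade and the shift from baseline grade for hemoglobin, platelets and ANC. Use the scheduled CBCs in all treated patients, regardless of attribution or AE status.
2. In Section 15.4, list and count all deaths from first dose to 30 days after last dose, by time and cause, regardless of attribution.
3. Reconcile 11.1 with 11.2, 11.4 and 11.8 so that a disease death is recorded the same way at every site. Check the wording of 11.5 on progression in the same edit.

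The cost is two extra tables from data already collected and a short edit to Section 11. Reported hematologic toxicity may look less favourable, since the grade and shift table will include disease-driven falls in count. Showing it beside the attributed AE counts lets readers see both.
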